6.5 Withdrawal of individual subjects

Specific criteria for withdrawal

Subjects can end their participation in the study at any time for any reason if they wish to do so without any consequences. The investigator can decide to withdraw a subject from the study for urgent medical reasons.

6.6 Replacement of individual subjects after withdrawal

During the inclusion period, additional patients will be included to be able to achieve the necessary number of patients in case of withdrawal of patients during the study.

6.7 Follow-up of subjects withdrawn from treatment

When patients withdraw from the study after time point 3, these data may (if authorized by the patient) be used for analyses.

6.8 Premature termination of the study

Situations in which the study should be terminated prematurely are not expected. Moreover, the use of 'usual care' and the FoodforCare products bring no additional risk to the patients. Therefore, we do not expect a large number of adverse events in either group.

7. PATIENT SAFETY

7.1 Section 10 WMO event

In accordance to section 10, subsection 1, of the WMO, the investigator will inform the subjects and the reviewing accredited METC if anything occurs, on the basis of which it appears that the disadvantages of participation may be significantly greater than was foreseen in the research proposal. The study will be suspended pending further review by the accredited METC, except insofar as suspension would jeopardise the subjects' health. The investigator will take care that all subjects are kept informed.

7.2 AEs, SAEs and SUSARs

7.2.1 Adverse events (AEs)

Adverse events are defined as any undesirable experience occurring to a subject during the study, whether or not considered related to the Food for Care products. All adverse events reported spontaneously by the subject or observed by the investigator or his staff will be recorded.

Our proposition will be to only register adverse events that have a possible causal relationship with the given food products. Examples of these events include gastrointestinal complaints and allergic reactions.

7.2.2 Serious adverse events (SAEs)

A serious adverse event is any untoward medical occurrence or effect that at any dose:

- results in death;
- is life threatening (at the time of the event);
- requires hospitalisation or prolongation of existing inpatients' hospitalisation;
- results in persistent or significant disability or incapacity;
- is a congenital anomaly or birth defect;
- Any other important medical event that may not result in death, be life threatening, or require hospitalization, may be considered a serious adverse experience when, based upon appropriate medical judgement, the event may jeopardize the subject or may require an intervention to prevent one of the outcomes listed above.

Our proposition will be to only register serious adverse events that have a possible causal relationship with the given food products. Examples of these events include gastrointestinal complaints and allergic reactions, which cause the above mentioned.

7.2.3 Suspected unexpected serious adverse reactions (SUSARs)

Not applicable for this study.

7.3 Follow-up of adverse events

All AEs will be followed until they have abated, or until a stable situation has been reached. Depending on the event, follow-up may require additional tests or medical procedures as indicated, and/or referral to the general physician or a medical specialist. (S)AEs will be reported till the end of study.

8. STATISTICAL ANALYSIS

8.1 Descriptive statistics

Nominal and ordinal variables will be described using frequency tables, modus and medians. Continuous variables will be described in terms of means and confidence intervals or with medians and range, dependent on normality of the data.

Data will be analyzed using IBM SPSS version 22 for descriptive and statistical analyses. All analyses will be performed according to the intention-to-treat principle.

8.2 Primary study parameter(s)

The primary study parameter is the change in hand grip strength between baseline and the end of the interventions, in percentages, compared to the control and the intervention group. This difference in percentages is a continue variable and will be compared by using the ANCOVA test.

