3.2 Randomization and blinding

The researcher will randomize the patient by using a password-protected randomization service which is part of the clinical data management system "Research Manager". Participants are randomized to either the intervention or the control group, using block randomization, stratified for underlying disease and MUST score (MUST1 or MUST $>$ 1). After randomization, the system provides a trial participants number, who will be documented in a designated source document with the patient information. The study number and birth date will be listed on all study documents. Blinding seems not possible for the coordinating researcher, since one group will receive FoodforCare and the other group will receive no additional products. Whether blinding is possible for the researcher will be examined during the pilot study. In that case, patients will be asked not to tell the researcher in which group they are allocated. Patients have to be aware of the group allocation. Any important protocol modifications will be communicated with the Medical Ethics Committee.

Figure 1. Study design

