4.4 Sample size calculation

The sample size calculation is based on the primary outcome of this study: the change in handgrip strength after 3 weeks between the groups. Based on literature and data from our previous study, patients will have a baseline handgrip strength of 28kg with a standard deviation of 5kg.(6) Assuming a difference of 2kg (7%) is a clinically relevant difference in favor of FoodforCare, we estimate that 209 patients are needed in order to obtain a power of 80% (two-tailed t-test, alpha 0.05). 251 patients should be included, assuming a drop-out rate of 20%. In order to improve the power significantly, we will make use of the ANCOVA test. By multiplying the number of patient with $(1-(\rho^2))$ a total of 228 patients will be needed. The correlation between the baseline and end of treatment (ρ) is estimated at 0.3, also because of the heterogeneity of the substantiated studies.

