8.3 Secondary study parameter(s)

The change in the other parameters for nutritional status between baseline and the end of het intervention will be compared between the control group and the intervention group. The continue variables such as, the change in BMI, quality of life, functional status and patient satisfaction will be analysed by a t-test. The ordinal variable such as, the MUST score and the PG-SGA will be analysed with a Mann-Whitney-U test. The difference in number of patients with a complication will be analysed by a Chi-square test.

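### Section 8.2 tests percentage change in handgrip strength with no named covariate, while section 4.4 derives 228 patients and 80% power in kg for a baseline-adjusted ANCOVA

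*Combined protocol and SAP*

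**What the plan says.** All references are to the combined protocol and SAP.

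- **Section 8.2** defines the primary parameter as the change in grip strength from baseline to the end of the intervention, expressed as a percentage. On the method it says only: "This difference in percentages is a continue variable and will be compared by using the ANCOVA test". No covariate is named.
- **Section 4.4** works in kg, with baseline mean 28 kg and SD 5 kg. The target is also given as a percentage: "Assuming a difference of 2kg (7%) is a clinically relevant difference in favor of FoodforCare". The starting number is for an unadjusted comparison: "we estimate that 209 patients are needed in order to obtain a power of 80% (two-tailed t-test, alpha 0.05"). It then turns to adjustment: "In order to improve the power significantly, we will make use of the ANCOVA test". The number is multiplied by (1 − ρ²), where ρ is described as "The correlation between the baseline and end of treatment" and is set at 0.3. The result is 228.
- **Sections 2.1 and 6.1** define the outcome as a difference or change in handgrip strength and give no unit.
- **Section 3.2** describes randomisation "using block randomization, stratified for underlying disease and MUST score". Neither factor appears in 8.2.
- **Section 8.3** uses a different method for continuous secondary outcomes, for example "functional status and patient satisfaction will be analysed by a t-test".

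**The concern.** The sample size and the primary analysis describe different tests. The factor (1 − ρ²), with ρ the correlation between baseline and end-of-treatment grip, is the variance reduction from regressing end-of-treatment grip in kg on baseline grip. It does not transfer to percentage change, which divides each patient's change by that patient's own baseline and so has a different error structure. The 7% in 4.4 restates 2/28; it comes with no SD on the percentage scale.

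Two things are at stake. First, a reader cannot confirm 80% power for the test that 8.2 specifies. Second, the scale and covariates of the primary model are not fixed. Analysts following the plan could fit kg or per cent, with baseline, strata, both or neither, and obtain different estimates and p-values. Section 3 says participants and investigators cannot be blinded, and 3.2 leaves blinding of the researcher to a pilot. The model should therefore be fixed before data are seen.

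**Working it through.** **Inputs from section 4.4:** mean 28 kg, SD 5 kg, difference 2 kg, ρ = 0.3, two-sided α 0.05, power 80%, drop-out 20%. **Assumed, because not stated:** 1:1 allocation, normality, the same SD at both time points.

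**1. The plan's figure.** Its own chain gives 209 × 1.2 = 251, then 251 × (1 − 0.09) = 228. A direct derivation agrees. The t-test needs 100 per arm (normal approximation 2 × (1.96 + 0.842)² × 25/4 = 98.1, so 99), or 200 in total. Then 200 × 0.91 = 182 and 182/0.8 = 227.5, so 228. The intermediate 209 is not what a t-test gives, but the end figure stands.

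**2. Power in kg.** The residual SD is 5 × √0.91 = 4.77 kg. With 228 × 0.8 = 182 completers, the standard error is 4.77 × √(4/182) = 0.707 and 2/0.707 = 2.83. Power is about 80% (0.803 by noncentral t). So 228 supports the baseline-adjusted kg analysis.

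**3. Power for percentage change.** To first order, the SD of percentage change is 100 × 5 × √(2 − 2 × 0.3)/28 = 21.1 points; simulation gives about 23. Power with baseline as covariate depends on how the spread of follow-up grip varies with baseline, which the plan does not state. The simulation used X ~ N(28, 5) and Y = 28 + 0.3(X − 28) + e + effect, with SD(e) proportional to X^k and mean variance 25 × 0.91. The three patterns are k = 0 (constant), 0.5 (square root of baseline) and 1 (proportional to baseline). There were 60,000 replicates at ρ = 0.3 and 40,000 at other values.

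| Completers, effect, ρ | kg ANCOVA, k = 0 / 0.5 / 1 | % change with baseline, k = 0 / 0.5 / 1 |
|---|---|---|
| 182, +2 kg, 0.3 | 80 / 80 / 80% | 76 / 79 / 81% |
| 182, (2/28) × baseline, 0.3 | 80 / 80 / 80% | 74 / 76 / 79% |
| 182, follow-up × (1 + 2/28), 0.3 | 77 / 77 / 77% | 73 / 76 / 78% |
| 190, +2 kg, 0.3 | 82 / 82 / 82% | 78 / 81 / 83% |
| 228, +2 kg, 0.3 | 88 / 88 / 88% | 85 / 87 / 89% |
| 182, +2 kg, 0.41 | 83 / 83 / 84% | 81 / 83 / 85% |

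Repeat runs differ by up to about one point, so the ranges quoted elsewhere are 76–82% (182, additive), 73–79% (182, proportional) and 77–83% (190, additive). The 190 row is 228/1.2, the inflation that 4.4 uses. With 228 completers and follow-up × (1 + 2/28) at constant residual SD, percentage change gives 82%.

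The pattern is as expected. If residual SD is constant in kg, dividing by baseline makes the errors unequal and costs about 4 points. If residual SD is proportional to baseline, the division evens them out and nothing is lost.

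**4. Type I error.** With no effect and 182 completers, each fixed model rejects in about 5% of runs (kg 4.9–5.0%; percentage change with baseline 4.9–5.0%). Reporting the smaller p-value of those two gives about 6%. Adding unadjusted percentage change as a third option gives about 9%.

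**The case against.** The best defence is that the sections, read together, nearly settle the covariate. ANCOVA needs one, 4.4 ties it to the baseline correlation, and 8.3 uses t-tests elsewhere, so the choice looks deliberate. That stands. A reader might infer from the silence in 8.2 that percentage change would be compared without baseline, with power of only 56–59% at 182 completers. The wording does not support that reading, and those figures should carry no weight.

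The power loss is also small and its direction uncertain. At 190 completers the largest loss against 80% is 2 to 3 points for an additive effect. Section 6.6 says "additional patients will be included to be able to achieve the necessary number of patients in case of withdrawal"; if that means 228 completers, the shortfall disappears, although 6.6 does not define the number. A correlation above 0.3 would help as well. A reader might infer that the trial is underpowered, and the documents do not support that either.

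Nor is the kg analysis immune: it falls to 77% if the effect multiplies follow-up grip. A reader might also infer that the planned test has an inflated error rate. It does not; the 6–9% arises only if the model is chosen after the results are seen.

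What remains is that no passage names the covariate, states why 8.2 uses per cent when 4.4 uses kg, or gives an SD for percentage change.

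**Conclusion.** The mismatch is certain from the text: 8.2 specifies percentage change with an unnamed covariate, and 4.4 supports 80% power only for a kg analysis adjusted for baseline. It is chiefly a gap in consistency and pre-specification. The effect on power is secondary: on the likely reading at ρ = 0.3 and 182 completers, it runs from a loss of about 4 points to a gain of 1 or 2 for an additive effect. For a proportional effect power is 1 to 7 points below the planned 80%. These figures rest on 1:1 allocation, normality and assumed variance patterns. The break-even at ρ of about 0.41 is for an additive effect with constant residual SD. The point should be fixed, but it does not threaten the trial.

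**What to change.** In 8.2, state that the primary analysis is an ANCOVA of end-of-treatment (T2) handgrip strength in kg on treatment group, with baseline handgrip (kg) as covariate. Adjust also for the randomisation strata: underlying disease as coded in the randomisation system (3.2 does not list its levels) and MUST 1 versus >1. Report the adjusted mean difference in kg with its 95% confidence interval, and keep percentage change as a descriptive summary. Adjusting for the strata follows from the randomisation; no power gain is claimed for it. With baseline in the model, analysing T2 grip or the kg change gives the same treatment estimate, so this agrees with 2.1, 4.4 and 6.1.

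The cost is wording in 8.2, with no extra patients, visits or data. The small downside is a headline in kg instead of per cent. If per cent is kept as primary, name baseline as the covariate and restate the power in 4.4 on that scale, with an SD for percentage change.

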8.3 Secondary study parameter(s)

The change in the other parameters for nutritional status between baseline and the end of het intervention will be compared between the control group and the intervention group. The continue variables such as, the change in BMI, quality of life, functional status and patient satisfaction will be analysed by a t-test. The ordinal variable such as, the MUST score and the PG-SGA will be analysed with a Mann-Whitney-U test. The difference in number of patients with a complication will be analysed by a Chi-square test.

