6.2 Secondary outcomes

- Functional status: besides HGS, change in functional status will be evaluated with the Short Physical Performance Battery.
- Nutritional status: change in nutritional status will be assessed with the PG-SGA and measurements of body weight (table 1).(18) PG-SGA will be filled in by the patient and a member of the research team. Body weight will be measured on a calibrated weighting scale (type ..) in sober state. Relative weight changes will be presented as the percent weight change relative to the weight at baseline. Body Mass Index will be calculated.
- Nutritional intake: difference in nutritional intake (protein and energy) will be evaluated at every time point based on a 2-day food diary filled in by the patient. The food diary will be cross checked by a member of the research team and, if necessary, the patient will be called for clarification. The food items will be coded and calculated according to the Dutch Food Composition Table (NEVO, RIVM). During the pilot study, we will evaluate if a "symptom diary" should be assessed.
- Length of hospital stay and readmission: reported from the medical record of the patients.
- Postoperative complications: reported from the medical record of the patients and classified using the Clavien-Dindo classification.(19) Grade of severity is based on the type of treatment for the specific complication. Infectious complications will be reported based on the definition of the American College of Chest Physicians/Society of Critical Care Medicine Consensus Conference.(20)
- Quality of life: change of quality of life will we assessed with the SF-36 questionnaire filled in by the patients. The Caregiver Reaction Assessment will be filled in by their caregiver.(21)
- Patient satisfaction:
 - o Both groups will fill in a questionnaire with questions about their wellbeing and stress level regarding shopping and cooking of their meals.
 - o In the intervention group, the Net Promoter Score (NPS) with additional questions will be used to assess patient satisfaction in the intervention group at time point 3. The NPS is determined by asking the question: 'How likely is it

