6.3 Other outcomes

- **MUST:** the Malnutrition Universal Screening Tool will be used at baseline and end of treatment (T2) to determine the risk of malnutrition.
- **Adverse events:** Possible adverse events including nausea, vomiting and gastrointestinal complaints will be identified by the "symptom diary". Unless we do not expect serious adverse events to occur, patients will be asked to contact a staff member and the researcher directly when adverse events occur. We will only report (serious) adverse events that have a possible causal relationship with the given food products till the end of the study. All AEs will be followed until they have abated, or until a stable situation has been reached.

Table 1. Measurements at each time point

	T0		T1	T2	T3
	Preoperative out-patient clinic	Contact by telephone	Baseline	End of treatment	30 days after surgery
Patient information	X				
Informed consent		X			
Randomization		X			
Handgrip strength			X	X	
Weight			X	X	
PG-SGA			X	X	
Nutritional intake			X	X	
Satisfaction				X	
SF-36			X	X	X
SPPB			X	X	X
Postoperative complication					X
Adverse events			X	X	X

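### Section 8.3 plans unadjusted t-tests for BMI, quality of life and functional status, although baseline values are collected and ANCOVA would be at least as precise for a negligible cost

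*Combined protocol and SAP*

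**What the plan says.** Section 8.3 sets the test for the continuous secondary outcomes: "The continue variables such as, the change in BMI, quality of life, functional status and patient satisfaction will be analysed by a t-test". It mentions neither a baseline covariate nor the stratification factors. The section opens by describing change from baseline to the end of the intervention, and section 6.2 uses the same terms: "change in functional status will be evaluated with the Short Physical Performance Battery", and "change of quality of life will we assessed with the SF-36 questionnaire filled in by the patients". The natural reading is therefore a t-test on change scores.

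Three other places bear on this choice.

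- Section 6.3, "Table 1. Measurements at each time point", marks weight (from which BMI is derived), SF-36 and SPPB at both T1 and T2. Satisfaction is marked at T2 only.
- Section 4.4, on the primary outcome: "In order to improve the power significantly, we will make use of the ANCOVA test". Section 8.2 repeats ANCOVA for handgrip strength.
- Section 3.2 randomises "using block randomization, stratified for underlying disease and MUST score".

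No section plans baseline adjustment for the secondary outcomes.

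**The concern.** The plan gives a reason for using ANCOVA on the primary outcome, then does not apply it to outcomes measured at the same two visits. A change score subtracts the baseline in full, which fixes the baseline slope at 1. ANCOVA estimates that slope from the data. Unless the true slope is 1, the change score stays correlated with baseline. Part of any chance imbalance between arms then remains in the comparison, and the confidence interval is wider than it needs to be.

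BMI, SF-36 and SPPB have no sample-size calculation of their own. There is no basis for assuming that precision on them can be given away.

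A smaller wording point sits in the same sentence, which can be read as listing satisfaction among the changes although it has no baseline. Section 6.2 describes two instruments. One goes to both arms: "Both groups will fill in a questionnaire with questions about their wellbeing and stress level". The other is "the Net Promoter Score (NPS) with additional questions will be used to assess patient satisfaction in the intervention group at time point 3". Table 1 has no satisfaction mark at T3, so it is unclear which visit is meant.

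**Working it through.** **Inputs**
- ρ = 0.3 between baseline and end of treatment, for handgrip strength only (section 4.4).
- No ρ for BMI, SF-36 or SPPB appears anywhere, so a range of 0.3 to 0.95 is assumed.
- Planned total 228 with 20% drop-out (section 4.4). Assuming 1:1 allocation, 228 × 0.8 / 2 = 91.2, or about 91 per arm.

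**The plan's own ANCOVA step.** Section 4.4 multiplies by (1 − ρ²): 251 × (1 − 0.09) = 228.4, which reproduces its 228. The plan therefore already relies on the variance factor used below.

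**Reading A: t-test on change, equal variance σ² at T1 and T2.** In units common to both methods:
- change score: 2σ²(1 − ρ)
- ANCOVA: σ²(1 − ρ²)
- ratio: (1 − ρ²) / [2(1 − ρ)] = (1 + ρ)/2

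| ρ | Variance ratio | Variance saved | Change-score CI wider by 1/√ratio − 1 |
|---|---|---|---|
| 0.3 | 0.65 | 35% | 24% |
| 0.5 | 0.75 | 25% | 15.5% |
| 0.7 | 0.85 | 15% | 8.5% |
| 0.9 | 0.95 | 5% | 2.6% |
| 0.95 | 0.975 | 2.5% | 1.3% |

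At ρ = 0.3 the change-score test needs 1/0.65 = 1.54 times the patients for the same precision.

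**Unequal variances.** With k = SD(T2)/SD(T1), the ratio is k²(1 − ρ²) / (1 + k² − 2ρk). Denominator minus numerator is (1 − ρk)², which is never negative, so the ratio cannot exceed 1. At ρ = 0.7 it is 0.628 for k = 0.8, 0.85 for k = 1.0 and 0.966 for k = 1.2.

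**Reading B: t-test on T2 values.** The ratio is 1 − ρ², so the saving is 9% at ρ = 0.3, 25% at 0.5, 49% at 0.7 and 81% at 0.9. This is the less natural reading. It is shown because the conclusion is the same under either one.

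**Cost of estimating the slope.** With 182 patients the ANCOVA variance is multiplied by about 1 + 1/(182 − 4) = 1.0056. The Reading A ratios become 0.654 at ρ = 0.3, 0.855 at 0.7, 0.981 at 0.95 and 1.001 at 0.99. The worst of these is a loss of about 0.1%.

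**Simulation at 91 per arm.** In 20,000 trials per value, the variance ratios were 0.645 (ρ = 0.3), 0.851 (0.7), 0.982 (0.95) and 1.001 (0.99). In 8,000 null trials, the mean estimates of both methods lay within 0.001 SD of zero, so neither is biased.

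**Illustration of power.** For an assumed difference of 0.4 SD and 91 per arm, the change-score t-test and ANCOVA have power of 62.1% and 80.1% at ρ = 0.3, 76.5% and 87.1% at 0.5, and 93.4% and 96.3% at 0.7.

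**The case against.** The strongest reply is that nothing here is wrong. A t-test on change is unbiased under randomisation, it already uses the T1 value, and these are secondary outcomes with no power claim. The gain is of unknown size, because the only documented ρ belongs to handgrip strength. For BMI, if ρ is 0.9 to 0.95, the saving is only 2.5% to 5% of the variance. All of this stands. It limits the point to one of efficiency, but it gives no reason to prefer the less precise test.

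Other objections stand in part:

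- The large savings under Reading B belong to a reading that the text hardly supports. They should not be taken as the expected gain.
- Section 8.2 applies ANCOVA to percentage change and names no covariate, so baseline adjustment of the primary is inferred from section 4.4. The inference is strong, because the factor (1 − ρ²) has no other meaning there.
- Section 3.2 does not list the levels of underlying disease, and several levels would use more than one degree of freedom. The levels must exist for the stratified randomisation to run, and at about 182 patients a few extra coefficients cost little.
- SF-36 and SPPB are also marked at T3, and protein and energy intake is also measured at T1 and T2. Section 8.3 concerns change to the end of the intervention, so a T2 analysis matches it. Leaving out intake limits the scope of the fix but does not undermine it.
- The NPS is already confined to the intervention arm, and its time point 3 may simply mean the third of T0, T1 and T2. This is a labelling query and no part of the case for ANCOVA.

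**Conclusion.** The concern holds as a recommended improvement; it does not question validity. Under either reading of section 8.3, ANCOVA with the T1 value as covariate is at least as precise as the planned t-test, apart from the degrees of freedom spent on covariates.

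Against the natural reading, the variance saved falls from 35% to 2.5% as ρ rises from 0.3 to 0.95, assuming equal variances at T1 and T2. The actual gain for each outcome is unknown because the plan gives no correlation for it. It is probably small for BMI and would be larger for SF-36 and SPPB if their correlations are lower. Allocation of 1:1 and about 91 analysed per arm are assumed for the finite-sample figures only.

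**What to change.** Replace the t-test sentence in section 8.3, for the outcomes that have a baseline, with:

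> BMI/weight, SF-36 scores and SPPB at T2 are compared between arms by ANCOVA, adjusting for the T1 value and the randomisation stratification factors (underlying disease, MUST 1 or >1).

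If the sponsor prefers to report change, ANCOVA of the absolute change with the T1 value as covariate gives the same treatment estimate. The levels of underlying disease should be written as they are used in the randomisation system. The same sentence could be extended to protein and energy intake.

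As a clarification, state that the T2 scores of the satisfaction questionnaire given to both arms are compared without a change score and that the NPS is descriptive in the intervention arm. Also reconcile its time point 3 with the T2 mark in Table 1.

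The cost is wording in the analysis section. The T1 values and stratification factors are already collected, so no visit, measurement or patient is added. Fixing the model in advance also removes a later choice between adjusted and unadjusted results.

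### PG-SGA and MUST are compared by a Mann-Whitney test with neither the baseline score nor the randomisation strata as covariates: valid, but it gives up power that data already collected could recover

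*Combined protocol and SAP*

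**What the plan says.** Section 8.3 opens with a general rule for the nutritional-status parameters: "The change in the other parameters for nutritional status between baseline and the end of het intervention will be compared" between the two arms. It then assigns tests by variable type. For the two scores at issue: "The ordinal variable such as, the MUST score and the PG-SGA will be analysed with a Mann-Whitney-U test". No covariate, stratum or adjusted analysis is named for them there or elsewhere.

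The data for an adjusted analysis are collected. On MUST, section 6.3 says that it "will be used at baseline and end of treatment (T2) to determine the risk of malnutrition". On PG-SGA, section 6.2 says that "change in nutritional status will be assessed with the PG-SGA and measurements of body weight (table 1"), and Table 1 marks PG-SGA at T1 and T2. Section 3.2 allocates patients "using block randomization, stratified for underlying disease and MUST score", with MUST split at 1 versus above 1.

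The two scores differ in standing. Section 2.2, objective 2, names weight and PG-SGA. MUST appears only under section 6.3, Other outcomes.

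**The concern.** A change score removes the baseline with a fixed coefficient of one. Unless the baseline-to-T2 correlation is very high, that over-corrects and adds noise, and fitting the baseline as a covariate does better. Separately, when allocation is balanced on a factor related to the outcome, a test that leaves the factor out works with too large a variance. Its true error then falls below 5% and power falls with it.

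The plan accepts this reasoning for handgrip strength: section 4.4 adopts ANCOVA to gain power and cuts the sample size on that basis. Section 8.3 gives no reason for forgoing the same gain on the ordinal scores. At stake is the ability to detect an effect on PG-SGA, one of the two measures named for secondary objective 2.

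**Working it through.** **Inputs from the documents.** Two-sided alpha 0.05, 80% power, 209 patients, 20% drop-out, correlation 0.3 and final total 228 (section 4.4, all for handgrip strength); stratification factors (section 3.2). No SD, effect or correlation is given for MUST or PG-SGA.

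**The plan's own figure.** Section 4.4 says "we estimate that 209 patients are needed in order to obtain a power of 80% (two-tailed t-test, alpha 0.05"). With 7% of 28 kg = 1.96 kg and SD 5 kg, the total is 206 (normal) or 208 (t-test), close to 209. Then 209 × 1.2 = 251 and 251 × (1 − 0.3²) = 228. This concerns handgrip only; it is used here to fix the number evaluable: 228 × 0.8 = 182, or 91 per arm.

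**Normal-theory guide.** With unit variance at both times, the variance is 2(1 − ρ) for a change score and 1 − ρ² after baseline adjustment. The relative efficiency of the change score is (1 − ρ²)/(2(1 − ρ)) = (1 + ρ)/2.

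| ρ | Efficiency | 182 patients are worth |
|---|---|---|
| 0.3 | 0.65 | 118 |
| 0.5 | 0.75 | 137 |
| 0.7 | 0.85 | 155 |
| 0.9 | 0.95 | 173 |

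For a 0.4 SD effect, power is Φ(0.4·√(91/2)/√v − 1.96), where v is the relevant variance. At ρ = 0.3 this is 0.63 (change) against 0.81 (adjusted); at ρ = 0.5 it is 0.77 against 0.88.

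**Simulated power, PG-SGA.** Assumptions: 182 patients, allocation balanced within strata, an integer-valued PG-SGA score only partly correlated with MUST, and Mann-Whitney on change against rank ANCOVA with baseline and strata. The effect was set at 2 × 2.80 × √(1 − ρ²)/√182 SD, the size at which a normal-theory adjusted analysis has 80% power (0.40, 0.36 and 0.30 SD at ρ = 0.3, 0.5 and 0.7).

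| ρ | Mann-Whitney on change | Rank ANCOVA |
|---|---|---|
| 0.3 | 0.58 | 0.77 |
| 0.5 | 0.63 | 0.76 |
| 0.7 | 0.69 | 0.74 |
| 0.9 | no loss | no loss |

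A second run held the effect at 0.4 SD, used permuted blocks of four within MUST (two levels) × four assumed disease groups, and took a correlation of 0.5 between PG-SGA and the latent MUST score. The Monte Carlo standard error is under 0.01.

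| ρ | PG-SGA: Mann-Whitney / rank ANCOVA | MUST: Mann-Whitney / rank ANCOVA |
|---|---|---|
| 0.3 | 0.58 / 0.76 | 0.60 / 0.74 |
| 0.5 | 0.73 / 0.84 | 0.75 / 0.82 |
| 0.7 | 0.92 / 0.94 | 0.90 / 0.92 |
| 0.9 (effect 0.25 SD) | 0.94 / 0.93 | 0.86 / 0.86 |

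**Simulated true error of Mann-Whitney on change (nominal 0.05), same run.** MUST: 0.030, 0.036 and 0.042 at ρ = 0.3, 0.5 and 0.7. PG-SGA: 0.043, 0.043 and 0.047. Both are 0.051 at ρ = 0.9. The Monte Carlo standard error is about 0.003.

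**Is stratifying alone enough?** For PG-SGA a van Elteren test on change has power 0.60, 0.73 and 0.92 at ρ = 0.3, 0.5 and 0.7, almost the same as the unstratified test. The gain comes from the baseline covariate.

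**If section 8.3 means the T2 score.** The Mann-Whitney sentence does not itself say change. Tested on T2 scores, PG-SGA power at 0.4 SD is 0.74, 0.73 and 0.75 against 0.76, 0.84 and 0.94, so the loss then grows with ρ. The error for MUST falls from 0.046 at ρ = 0.3 to 0.011 at ρ = 0.9.

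**The case against.** The strongest reply is that this is a choice of efficiency, not an error. A Mann-Whitney test on an ordinal outcome in a randomised trial is valid, and no power is claimed for these outcomes. The size of the loss rests on assumptions: the 0.3 in section 4.4 is for handgrip, and an interval of three weeks could plausibly give a high correlation, where the gain vanishes. The protocol also does not say whether PG-SGA is analysed as a category or as a numeric score, and the figures assume a numeric one. All of this stands. It limits the point to an optional improvement; it does not remove it, because the cost is so low.

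Four stronger readings are tempting and are not supported.

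- *The test is conservative for both scores.* A simulation that treats PG-SGA and MUST as the same underlying measure gives PG-SGA errors of 2.0%, 2.7% and 3.8% at ρ = 0.3, 0.5 and 0.7. The documents give no basis for that. At a correlation of 0.5 between the two the errors are 4.3%, 4.8% and 4.8%, and at zero 4.7%, 4.9% and 4.9%.
- *The floor on MUST biases the comparison.* A patient starting at 1 can improve by one point at most, and one starting at 3 by three. Randomisation gives both arms the same expected distribution of starting scores, so this affects sensitivity and interpretation but does not create bias.
- *The analysis uses no baseline information.* A change score uses the baseline by construction; what is missing is the baseline as a covariate.
- *The power loss on MUST harms secondary objective 2.* That objective does not name MUST.

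**Conclusion.** The point holds as a low-priority improvement. The planned test keeps its error rate at or below nominal but is less powerful than a baseline- and stratum-adjusted rank analysis. For PG-SGA, the score that matters for a stated objective, the loss is about 19 points of power at ρ = 0.3 (0.77 − 0.58), 13 at 0.5 (0.76 − 0.63) and 5 at 0.7 (0.74 − 0.69), and nil at 0.9. Clear conservatism is confined to MUST, at about 3-4% for ρ from 0.3 to 0.7.

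These sizes assume 182 evaluable patients, approximately normal latent scores, the effects shown above, and change from baseline as the quantity tested. Replacement of withdrawn patients (section 6.6) could raise the number evaluable; the normal-theory efficiency ratio does not depend on it.

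**What to change.** In section 8.3, specify that the T2 PG-SGA and T2 MUST scores are each analysed by rank ANCOVA with arm, that score's baseline value, MUST stratum (1 or above 1) and underlying-disease group. Proportional-odds regression with the same terms is an alternative where proportional odds is tenable, and it gives an interpretable odds ratio. The gains above were computed for rank ANCOVA only; none was computed for the proportional-odds model. Keep the Mann-Whitney test as supportive, and say whether it is applied to change or to the T2 score. State also whether PG-SGA is analysed as a category or as a numeric score.

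The cost is a few lines of analysis text and slightly more analysis work, with no new data. The wording should be settled before outcome data are seen. The downside is little or no gain if the baseline-to-T2 correlation turns out near 0.9.
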